### **31) Statistical Analysis**

### **32) Sample Size Determination**

The study is planned to enroll at fifteen sites and will enroll until 115 subjects are identified with inadequate bowel prep.

Assuming a 12% inadequate prep rate 1067 patients would be enrolled to achieve 115 patients inadequate bowel preparation. The final sample size, however, will be determined by the number needed to undergo colonoscopy to achieve 115 and therefore may be greater than or less than 1067.

The sample size of 115 was determined to provide at least 90% power for the primary endpoint of demonstrating conversation rate of inadequate colonoscopies after the use of the Pure-Vu EVS System is greater than a 30% performance goal.

Assuming a true conversion rate of 50%, then 115 inadequately prepped patients undergoing Pure-Vu with the opportunity to convert to adequate prep will provide  $\geq 99\%$  power and at least 115 patients for safety. To be conservative, 115 inadequately prepped patients will provide  $\geq 90\%$  power to produce an exact 95% CI  $> 30\%$  even if the true conversion rate is 45%.

### **33) Description of Statistical Methods**

Basic demographic and other baseline characteristics will be collected and analyzed for all subjects. Unless specified otherwise, descriptive statistics will be presented for the total study population, by colonoscopy prep adequacy group, and overall. Subgroup analyses may occur, including but not limited to age group (40 to <65 vs 65 to 80), insurance type, site care location, and colonoscopy indication, all of which will be further described in the Statistical Analysis Plan (SAP). For

Document Title: Colonoscopy: Demonstrating Effective Salvage of Inadequate Colonoscopies Utilizing the Pure-Vu EVS System	Outpatient	Document No. CL00052	Amendment 2.0	Page 30 of 46
---	------------	--------------------------------	-------------------------	---------------

quantitative summaries, mean, standard deviation (SD), median, minimum, and maximum will be presented. For qualitative summaries, counts and percentages will be presented.

#### **34) Safety Population**

The safety population is defined as any subject presented for procedure and enrolled into the study. This population will be used for all safety analyses.

#### **35) Intent-to-Treat (ITT) Population**

The ITT population is defined as any subject who was able to proceed with an optical colonoscopy and have a complete procedure or an incomplete procedure solely due to inadequate bowel prep. This population will be used for all efficacy analyses. A completed procedure is defined as one with the ability to reach the cecum with OC either before or after Pure-Vu.

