Sample Size	
Subjects will be enrolled until 115 inadequate bowel prep cases via SOC are accrued and subsequently treated with Pure-Vu. 115 IBP cases provides 90% power and with an expected 12% inadequate bowel prep rate and accounting for 10% attrition, approximately 1,067 subjects will need to be enrolled to achieve 115 inadequate preps required Pure-Vu. A minimum of 50% of enrollees with inadequate bowel prep must utilize Medicare or Medicaid as their insurance provider.
 
The following assumptions were considered for sample size calculation:
 

• Performance goal for 30% reduction

• <math>\geq 90\%</math> Power and two-sided <math>\alpha = 0.05</math>

• True reduction in IBP vs. SOC = 50%

• <math>\sim 10\%</math> attrition rate

Planned # of Sites	Up to 15 clinical sites

Document Title: Colonoscopy: Demonstrating Effective Salvage of Inadequate Colonoscopies Utilizing the Pure-Vu EVS System	Outpatient	Document No. CL00052	Amendment 2.0	Page 9 of 46
---	------------	--------------------------------	-------------------------	--------------

Primary Endpoints	
Rate of incomplete colonoscopies due to inadequate preparation salvaged to adequate colonoscopies with the use of the Pure-Vu EVS System.
 
Inadequate OCs defined as such if any of the following are met:
 

▪ BBPS < 6 (Adequacy is defined as BBPS of 2 or greater in each segment)

▪ Inability to identify > 5mm polyps

 
The estimated rate of salvaged preparations will be calculated and presented with exact two-sided 95% confidence interval: Number of preps inadequate with SOC and adequate after Pure-VU EVS System / Number of preps inadequate with SOC.
 
The lower bound will be compared to a 30% performance goal.

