## **16) Primary Endpoint**

Rate of incomplete colonoscopies due to inadequate preparation salvaged to adequate colonoscopies with the use of the Pure-Vu EVS System.

Inadequate OCs defined as such if any of the following are met:

- BBPS < 6 (Adequacy is defined as BBPS of 2 or greater in each segment)
- Inability to identify > 5mm polyps

Document Title: Colonoscopy: Demonstrating Effective Salvage of Inadequate Colonoscopies Utilizing the Pure-Vu EVS System	Outpatient	Document No. CL00052	Amendment 2.0	Page 22 of 46
---	------------	--------------------------------	-------------------------	---------------

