## **29) Colonoscopy Procedure**

The insertion during the colonoscopy procedure will be performed by the clinical study investigator(s), experienced in GI endoscopy according to the local standard of care. The type of

Document Title: Colonoscopy: Demonstrating Effective Salvage of Inadequate Colonoscopies Utilizing the Pure-Vu EVS System	Outpatient	Document No. CL00052	Amendment 2.0	Page 28 of 46
---	------------	--------------------------------	-------------------------	---------------

sedation will not be dictated by the study but will be documented. The colonoscope will be prepared and the procedure will proceed per the standard of care.

During the procedure, the study endoscopist will be requested to document BBPS for each colon segment. Once the endoscopist notices an inadequate segment, the endoscopist should attempt to cleanse per his/her standard of care practices with the goal to achieve a BBPS of 2 or higher for that segment. This should be repeated for each colonic segment. If the study definition of inadequate is met in any segment, even after SOC cleansing, the endoscopist is required to take pictures of all accessed segment(s) including the inadequate segment(s). The endoscopist will withdraw the colonoscope and all procedural outcomes and findings should be documented. Then the Pure-Vu Oversleeve will be placed onto the colonoscope, and the procedure will be performed utilizing the Pure-Vu System for cleansing. Photo-documentation of each segment will be required to show BBPS after Pure-Vu use. Once the procedure has been completed with Pure-Vu, procedural outcomes (inclusive of final adequacy determination after Pure-Vu use and findings will be documented again.

If during the standard of care colonoscopy, the patient cannot proceed onto Pure-Vu and/or will be deemed an incomplete colonoscopy due to any reason other than inadequate prep, that subject will be withdrawn from the study. Such an instance might occur when a mass or stricture is found, or when an active inflammatory condition is detected but is it ultimately up to the Principal or Sub-Investigator to make the determination during the procedure.

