#### **36) Per Protocol (PP) Population**

The PP population is defined as any subject in the ITT who do not have any major protocol deviations and in whom the Pure-Vu system was utilized as planned. This population will also be used for all efficacy analyses.

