#### **37) Inadequate Bowel Preparation (IBP) Population**

The IBP population is defined as any subject that were identified to have inadequate prep after initial OC and were indicated for cleansing with the Pure-Vu System and did not have any major protocol deviations.

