#### **38) Primary Endpoint Analysis**

The primary endpoint is conversion rate of inadequate colonoscopies to adequate colonoscopies after the use of the Pure-Vu EVS System, where inadequate OCs defined as such if any of the following are met:

- BBPS < 6 (Adequacy is defined as BBPS of 2 or greater in each segment)
- Inability to identify >5mm polyps

Document Title: Colonoscopy: Demonstrating Effective Salvage of Inadequate Colonoscopies Utilizing the Pure-Vu EVS System	Outpatient	Document No. CL00052	Amendment 2.0	Page 31 of 46
---	------------	--------------------------------	-------------------------	---------------

The conversion rate,  $\theta$ , is defined as number of preps inadequate with SOC and adequate after Pure-VU EVS System divided by the number of preps inadequate with SOC.

$$H_0: \theta \leq 0.30$$

$$H_1: \theta > 0.30$$

The conversion rate and its two-sided 95% exact binomial interval will be presented and compared to the 30% performance goal. The proportion of preps inadequate after SOC and inadequate after SOC + Pure-Vu will also be reported.

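### The set named for all efficacy analyses can drop stopped Pure-Vu passes that the primary formula counts as not converted

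*Protocol*

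**What the plan says.** Protocol Section 35 defines the intent-to-treat (ITT) set by how the procedure ended. Members "have a complete procedure or an incomplete procedure solely due to inadequate bowel prep", and a completed procedure is "one with the ability to reach the cecum with OC either before or after Pure-Vu". The section assigns this set to all efficacy analyses, which includes the primary endpoint.

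The primary formula has no completion condition. The synopsis (Section 1) gives it as "Number of preps inadequate with SOC and adequate after Pure-VU EVS System / Number of preps inadequate with SOC". Section 38 repeats it, with conversions "divided by the number of preps inadequate with SOC", and names no analysis set.

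Four other places bear on the question:

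- Section 16 words the endpoint as "Rate of incomplete colonoscopies due to inadequate preparation salvaged to adequate colonoscopies", so there incomplete describes the state before Pure-Vu.
- Section 29 says that if, during the SOC colonoscopy, the subject cannot go on to Pure-Vu or is "deemed an incomplete colonoscopy due to any reason other than inadequate prep, that subject will be withdrawn from the study". It is silent on a pass stopped after Pure-Vu has begun.
- Section 36 restricts the per-protocol set further, to ITT members without major deviations and "in whom the Pure-Vu system was utilized as planned".
- Section 37 defines the inadequate-prep (IBP) set as those found inadequate after the initial colonoscopy who were "indicated for cleansing with the Pure-Vu System and did not have any major protocol deviations". The protocol ties this set to no analysis.

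**The concern.** A set called intent-to-treat should not depend on what happened once the device was in use. Take a subject whose prep is inadequate after SOC cleansing and whose cecum was not reached in the SOC pass. Pure-Vu is started, the pass is stopped because the scope cannot be advanced, the device malfunctions or a complication occurs, and the cecum is never reached. Sections 1 and 38 count this subject as not converted. Section 35, read over the whole procedure, removes the subject.

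The trial has one arm and a fixed goal, so the denominator is half of the result and no control group offsets an exclusion. If the removed attempts are failures, removing them can only raise the rate. The primary denominator should be settled before anyone sees data.

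**Working it through.** **1. The plan's own figures.** Inputs: n = 115, goal 30%, exact two-sided 95% interval (Sections 1, 32, 38). The Clopper-Pearson lower limit is 0.3016 for 45/115 and 0.2935 for 44/115, so success needs 45 conversions (39.1%). One-sided type I error is P(X ≥ 45 | 115, 0.30) = 2.28%. Power is 91.3% at a true rate of 45% and 99.3% at 50%, which agrees with the 90% and 99% in Section 32.

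**2. Who is affected.** All rows are SOC-inadequate subjects who start Pure-Vu.

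| Course | Formula, Sections 1 and 38 | Section 35, whole procedure | Section 35, SOC pass only |
|---|---|---|---|
| Still inadequate after a completed Pure-Vu pass | not converted | in | in |
| Cecum reached in SOC pass, Pure-Vu pass then stopped | not converted | in | in |
| Cecum not reached in SOC pass, Pure-Vu pass stopped for a non-prep reason, cecum never reached | not converted | **out** | in |

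Only the third row is in dispute.

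**3. Share dropped, f.** The protocol gives no rate for such stops. Section 9 gives an upper figure, the share in whom the cecum was not reached for any reason: 2.0% (98% reached), 1/47 = 2.1% (97.9% reached) and 2/83 = 2.4% (81/83 reached). The text prints 96% for 81/83, which is 97.6%; the counts are used here. These shares include prep failures and subjects adequate at baseline, so the true f should be lower.

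**4. False success at a true rate of 30%, every dropped case a failure.** With c(m) the smallest count out of m whose exact lower limit exceeds 30%:

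Σ over k of Bin(k; 115, f) × P(X ≥ c(115 − k)), where X ~ Bin(115 − k, 0.30/(1 − f)).

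| f | False success |
|---|---|
| 0 | 2.28% |
| 0.5% (assumed) | 2.30% |
| 1.0% (assumed) | 2.38% |
| 1.5% (assumed) | 2.54% |
| 2.0% | 2.73% |
| 2.1% | 2.79% |
| 2.4% (about 2.8 of 115) | 2.92% |

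It reaches the nominal 2.5% at about f = 1.4%. At an assumed 5%, above anything the prior studies show, it would be 4.4%.

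**5. Chance that the drop turns a fail into a pass.** Σ over k of Bin(k; 115, f) × P(c(115 − k) ≤ X ≤ 44), where X ~ Bin(115 − k, p/(1 − f)).

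| f | True rate p = 45% | p = 50% |
|---|---|---|
| 1.0% | 0.4% | 0.05% |
| 2.4% | 1.8% | 0.2% |

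**6. At the threshold.** With 44 conversions the lower limit is 29.4% of 115, 29.6% of 114 and 29.9% of 113, all fails. With three drops, 44/112 gives 30.2% and passes. With 43 conversions six drops are needed (43/109, 30.2%).

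**7. Where the result may lie.** In the inpatient study adequacy rose from 32/84 to 81/84. If none regressed, 81 − 32 = 49 of 84 − 32 = 52 converted (94%), far above 45/115.

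**The case against.** The strongest reply is that Section 35 borrows the language of Sections 16 and 29, where incomplete refers to the SOC stage. Read that way, every SOC-inadequate subject who goes on to Pure-Vu stays in. This reading is possible. But Section 35's own definition of completion looks past the SOC pass, and a set cannot comfortably judge complete over the whole procedure and incomplete over only the first part. What stands is that the text is ambiguous; the whole-procedure reading remains the more natural one.

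It can also be said that applying a formula within an analysis set is ordinary practice. That is so, but here the set removes failures that the formula's stated denominator includes.

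The group is narrow, and this point stands. In the inpatient study 71/83 reached the cecum with Pure-Vu but 81/83 reached it at all, so 10 of the 12 who did not reach it with the device still counted as reached. The prior rates also come from Generation 1 studies, in inpatients or after deliberately reduced preparation. Both facts limit the size, and for that reason 2.4% is used only as an upper figure.

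Handling of missing results is often left to an analysis plan. Here, however, the protocol itself defines the sets, assigns one to all efficacy analyses and prints the formula. An analysis plan that followed the whole-procedure set would depart from the printed denominator, and the reverse.

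**Conclusion.** The concern holds and should be fixed, with medium confidence because a second reading exists. On the natural reading, Section 35 removes stopped Pure-Vu attempts that Sections 1 and 38 count as failures; on the other reading it does not. Sections 29, 36 and 37 do not settle which applies.

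The effect is small. Over the range the documents support, false success stays between 2.28% and 2.92%, and at the planning rates the chance of a changed verdict is at most 1.8%. This assumes that all dropped cases are failures, that drops are binomial with share f, and that f does not exceed the prior cecal non-intubation rates. Conversion near the prior inpatient figure would leave the verdict untouched.

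**What to change.** In the synopsis and Sections 35, 37 and 38, name one primary analysis set: all subjects with prep inadequate after SOC cleansing who were not withdrawn during the SOC pass under Section 29, whether or not the Pure-Vu pass was completed and regardless of protocol deviations. Count anyone without documented adequacy after Pure-Vu as not converted.

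This set is still slightly narrower than the literal denominator of Sections 1 and 38. Add a sensitivity analysis on that denominator, counting SOC-inadequate subjects withdrawn during the SOC pass as failures and listing them by reason. In Section 35, state whether incomplete refers to the SOC pass or the whole procedure. Keep the current ITT, per-protocol and deviation-free IBP sets as supportive.

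The cost is wording only, with no extra patients or data; the reported rate may be slightly lower. Power at n = 115 stays 91.3% (true 45%) and 99.3% (true 50%) if the planning rates cover all SOC-inadequate subjects. If they were meant among completed procedures only:

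- Counting 1% as failures gives rates of 0.45 × 0.99 = 0.4455 and 0.50 × 0.99 = 0.495, with power 89.7% and 99.0%.
- Counting 2.4% gives 0.45 × 81/83 = 0.4392 and 0.50 × 81/83 = 0.4880, with power 87.1% and 98.5%.

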## 17) Secondary Endpoints

The following secondary endpoints will be assessed:

1. Number of polyps and adenomas: type, location, size, pathology, and morphology, as well as:
  - Polyp Detection Rate (PDR)
  - Polyp Miss Rate (PMR)
  - Adenoma Detection Rate (ADR)
  - Adenoma Miss Rate (AMR)
  - Adenoma Per Colonoscopy (APC)
  - Adenomas Per Positive Patient (APP)
  - Sessile Serrated Adenoma Detection Rate
2. Boston Bowel Preparation Score (BBPS) before and after Pure-Vu EVS use
3. Other Procedural Outcomes (including but not limited to):
  - Sedation type
  - Procedure time: time to cecum and withdrawal time including additional time necessary to perform Pure-Vu EVS, in cases where Pure-Vu is utilized.
  - Intraprocedural tools
4. Cecum Intubation Rate
5. Compliance to published interval guidelines for surveillance or repeat screening  
(Prescribed intervals per USMSTF)

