### **39) Secondary Endpoint Analysis**

All secondary endpoints will be summarized using descriptive statistics and full details on additional planned analyses will be provided in the prospective Statistical Analysis Plan.

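### Cecum intubation rate is analysed in a population selected on reaching the cecum, which inflates the rate and leaves only prep-related failures in it

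*Protocol*

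**What the plan says.** Protocol section 17 lists "Cecum Intubation Rate" as the fourth secondary endpoint, without a formula or a denominator. Section 39 deals with the analysis: "All secondary endpoints will be summarized using descriptive statistics and full details on additional planned analyses will be provided" in the SAP.

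The population is fixed in section 35. The ITT consists of subjects who could proceed with colonoscopy and "have a complete procedure or an incomplete procedure solely due to inadequate bowel prep. This population will be used for all efficacy analyses". The same section adds: "A completed procedure is defined as one with the ability to reach the cecum with OC either before or after Pure-Vu".

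Section 36 builds the second efficacy set on the first: "The PP population is defined as any subject in the ITT who do not have any major protocol deviations".

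Section 29 also removes subjects during the procedure. A subject who cannot go on to Pure-Vu, or whose SOC examination "will be deemed an incomplete colonoscopy due to any reason other than inadequate prep, that subject will be withdrawn from the study", leaves the study. For those who do go on to Pure-Vu, outcomes are recorded at the end of the SOC pass ("The endoscopist will withdraw the colonoscope and all procedural outcomes and findings should be documented") and once more after the Pure-Vu pass.

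Section 37 defines an IBP population as "any subject that were identified to have inadequate prep after initial OC and were indicated for cleansing with the Pure-Vu System", without major deviations. That set does not depend on reaching the cecum, but the protocol assigns no analysis to it.

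**The concern.** A rate is informative only if subjects enter its denominator regardless of the outcome. Here entry depends on whether the cecum was reached and, if not, why. Someone not reached because of looping, anatomy, sedation or difficulty advancing the sleeved colonoscope is not counted as a failure but is removed from the calculation.

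The secondary objective is the impact of Pure-Vu on patient outcomes, and whether the colonoscope reaches the cecum is a basic performance measure for a device mounted over it. A rate near 100% that results partly from the entry rule could be taken as evidence of performance. It would also invite comparison with the cecum intubation rates in section 9, which rest on different denominators.

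**Working it through.** **1. Who can be in the ITT, and how they score**

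| Subject | In the ITT? | Contribution to cecum intubation rate |
|---|---|---|
| Adequate prep, cecum reached | Yes | Success |
| Adequate prep, cecum not reached | No: the reason cannot be prep | Removed |
| Inadequate prep, cecum reached on SOC pass, not on Pure-Vu pass | Yes: reached on one pass | Depends on how the endpoint is scored; not stated |
| Inadequate prep, missed on SOC pass, reached on Pure-Vu pass | Yes | Success after Pure-Vu |
| Inadequate prep, missed on both passes because of prep alone | Yes | Failure |
| Inadequate prep, missed on SOC pass, then missed on Pure-Vu pass for a non-prep reason | No: prep is not the sole reason | Removed |

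Rows 1 and 2 give 100% by definition in the adequately prepped group. This matters because section 33 presents descriptive results by prep adequacy group. Row 6 is where a device-related failure can disappear.

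**2. The plan's own figures**

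The protocol states no expected cecum intubation rate, so there is none to reproduce. The planned enrolment serves below as a scale: 115 / 0.9 = 127.8, rounded up to 128; 128 / 0.12 = 1,066.7, rounded up to 1,067, as stated.

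**3. Size of the inflation**

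Let *a* be the proportion of attempted procedures that miss the cecum for a non-prep reason, *b* the proportion that miss it on the SOC pass because of prep, and *s* the share of the latter rescued by Pure-Vu. None of these is in the protocol; all are assumptions. Write *f* = *b* before Pure-Vu and *f* = *b*(1 − *s*) after.

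- All attempted: rate = 1 − *a* − *f*
- ITT: rate = 1 − *f* / (1 − *a*)
- Difference = *a* × (1 − *f* / (1 − *a*)), that is, *a* times the ITT rate

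With *b* = 6% and *s* = 50%:

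| *a* | All attempted, before → after | ITT, before → after | Inflation after |
|---|---|---|---|
| 1% | 93.0% → 96.0% | 93.9% → 97.0% | 1.0 point |
| 2% | 92.0% → 95.0% | 93.9% → 96.9% | 1.9 points |
| 5% | 89.0% → 92.0% | 93.7% → 96.8% | 4.8 points |

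If all prep failures are rescued (*s* = 100%), the ITT shows 100% in every row, against 99%, 98% and 95% in all attempted. The before/after gain is nearly unchanged: 3.0 points in all attempted, and 0.03 / 0.95 = 3.2 points in the ITT at *a* = 5%. So the level is distorted much more than the change.

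On 1,067 procedures, 1% to 5% is about 11 to 53 subjects removed. If the 10% attrition is taken off first (1,067 × 0.9 = 960), it is about 10 to 48.

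**4. The Pure-Vu group**

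Let *u* be the share of the 115 cases missed on the SOC pass, and *d* the share of those missed on the Pure-Vu pass for a non-prep reason. The number removed is 115 × *u* × *d*. With *u* from 25% to 100% and *d* from 1% to 5% (assumptions), this runs from 115 × 0.25 × 0.01 = 0.3 to 115 × 1.00 × 0.05 = 5.8 subjects. If there are no other failures and reaching the cecum on either pass counts, the rate over all 115 is 1 − *ud*, or 99.75% down to 95.0%. The ITT gives 100% throughout.

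**The case against.** The endpoint is descriptive, has no target, and its details are left to an SAP that is not shown. The failures that Pure-Vu is meant to convert are prep-related, and these stay in the ITT. Section 33 also presents descriptive statistics for the total study population unless specified otherwise, so the ITT may not govern this endpoint.

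Much of this stands and limits the point. The reference to the SAP does not remove it, because section 35 leaves no choice of population: it names the ITT for all efficacy analyses. Cecum intubation is not among the safety endpoints, which have their own population in section 34. Section 33 yields by its own terms where something else is specified. If it is nevertheless thought to govern, the two sections disagree and the denominator still has to be stated.

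A reader might go further and infer any of the following, which the documents do not support:

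- *The rate cannot show any effect of Pure-Vu, or cannot fall because of the device.* Prep failures remain, so a gain is visible. A subject reached on the SOC pass but not with the Oversleeve also remains, so a rate reported per pass would show that loss.
- *Every failed Pure-Vu pass is hidden when the SOC pass succeeded.* The either-pass sentence defines a completed procedure for ITT entry. The protocol does not say that the endpoint is scored that way.
- *The ITT rule could turn about 86% into 100%, some 17 of 115 subjects.* In the Generation 1 inpatient study in section 9, 81/83 (97.6%, printed as 96%) reached the cecum and 71/83 (85.5%) did so using Pure-Vu. Of the 12 not reached with Pure-Vu, 10 were reached otherwise and would stay in an ITT defined as here. At most 2/83 could drop out, or 2/83 × 115 = about 3 subjects, and only if neither failure was prep-related. The causes are not given.
- *The section 9 rates were unfiltered.* The inpatient study excluded one patient for a condition found during the procedure, and 11 of 94 procedures that ended in a diagnosis before the cecum were left out to give the 83. For the two outpatient studies the protocol does not say.

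**Conclusion.** The point holds as a bias in the level of one descriptive secondary endpoint. It follows from the wording of sections 35 and 36 that the rate is 100% by definition in adequately prepped subjects, that overall it reflects only prep-related failures, and that non-prep failures on the Pure-Vu pass are lost in subjects whose SOC pass also missed the cecum. Whether the remaining information on Pure-Vu is visible depends on reporting the rate per pass, which the protocol does not require.

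The inflation is roughly equal to the non-prep failure rate: about 1 to 5 points if that rate is 1% to 5%. That range is an assumption. The primary comparison with the 30% goal, its power and the requirement of 115 cases are unaffected. The change is worth making because a biased rate is fixed in the protocol and is cheap to correct.

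**What to change.** In sections 35 and 39, exempt cecum intubation rate from the ITT and PP populations and report it per pass:

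- SOC pass: denominator is every subject in whom the colonoscope was inserted.
- Pure-Vu pass: denominator is every subject in whom use of the Oversleeve was attempted.

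Keep subjects withdrawn under section 29 in the denominator of each pass they underwent, classify them by whether the cecum was actually reached on that pass, and list the reasons for failure. They should not all be scored as not reached: section 29 also withdraws subjects who cannot go on to Pure-Vu, and some of these may have been reached on the SOC pass.

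The cost is wording in the protocol and SAP, and keeping the procedural outcomes of withdrawn subjects in the database. Section 29 already calls for outcomes to be documented before and again after Pure-Vu, so little new data collection is needed. The reported rate will be slightly less favourable.
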